11.3 Electrocardiogram

A central vendor with readers blinded to treatment assignment will perform the reading of the ECGs. The central ECG results will be used for the statistical analyses.

Descriptive statistics for ECG parameters (heart rate, RR interval, PR interval, QRS interval, QT interval, and QTc interval) at baseline and at the EOT Visit, and the change from baseline will be presented by treatment group. The QTc interval will be presented by both the Bazett ($QTcB = QT/(RR)^{1/2}$) and the Fridericia ($QTcF = QT/(RR)^{1/3}$) corrections. The change from baseline to the minimum and maximum post-baseline values (including EOT and any unscheduled post-baseline assessments) will also be summarized by treatment group. Baseline is defined as the value closest to but prior to the initiation of test article administration. If no value is available prior to the initiation of test article administration, a value within 2 hours after initiation of test article administration can be used as baseline.

The number and percentage of subjects with any post-baseline (including EOT and any unscheduled post-baseline assessments) increase in QTcF and any post-baseline increase of > 30 msec or > 60 msec in QTcF will be summarized by treatment group. The number and percentage of subjects with a baseline QTcF \leq 450 msec and with a post-baseline QTcF of > 450 msec and with a baseline QTcF \leq 500 and with a post-baseline QTcF of > 500 msec will also be summarized by treatment group. The number and percentage of subjects with a post-baseline increase in QTcF of > 30 msec resulting in a post-baseline QTcF of > 450 msec or > 500 msec will also be summarized by treatment group. A listing will also be provided of subjects with a QTcF that meets one of the criteria listed above and will list all QTcF values for the subject.

The distribution of QTcF values (\leq 450 msec, > 450 to \leq 480 msec, > 480 to \leq 500 msec, and > 500 msec) at each time point and the distribution of change from baseline in QTcF values at EOT (0 or less [no increase], 1 to 29 msec, 30 to 60 msec, and > 60 msec) will be summarized by treatment group.

11.4 Laboratory Values

Summaries of laboratory data will include hematology, chemistry and coagulation (INR only) parameters. Laboratory parameters will be presented in alphabetic order with the following exceptions: differentials of white blood cell (WBC) counts will be presented following the WBC results, and chemistry parameters will first be grouped by organ class (renal, liver, electrolytes, and other) and presented alphabetically within each of these classes, as shown in [Table 9](#).

Table 9. Laboratory Parameters and Organ Class

Organ Class	Laboratory Parameter
Renal	Creatinine
Renal	Urea
Liver	Alkaline phosphatase (ALP)
Liver	ALT
Liver	AST
Liver	Total Bilirubin
Liver	GGT
Electrolytes	Bicarbonate
Electrolytes	Calcium
Electrolytes	Chloride
Electrolytes	Magnesium
Electrolytes	Potassium
Electrolytes	Sodium
Other	Albumin
Other	Amylase
Other	Blood glucose
Other	Cholesterol
Other	CK
Other	CK isoenzyme
Other	LDH
Other	Lipase
Other	Phosphate
Other	Total protein
Other	Uric acid

Baseline is defined as the central lab value closest to and prior to the first dose of test article. If no central lab value is available prior to the first dose of test article the local lab value that is closest to and prior to the first dose of test article will be used as baseline. For by visit analyses, central lab values will be used unless no central lab value was obtained in the visit window. In this case, local lab values will be used for the by visit analyses. All lab values (central and local) are used for determination of the overall worst post-baseline value.

Several analyses of the laboratory data will be presented. Descriptive statistics (based on SI units) for chemistry and hematology values and the change from baseline will be summarized by treatment group at each time point (Day 3 [+ 1 day], Day 7 [+1 day], Day 10 [+1 day], EOT visit and PTE visit), and for the overall worst value post-baseline (which includes unscheduled visits). [Appendix 4](#) provides the directionality of the worst values for each laboratory parameter.

Clinically notable laboratory values will be determined based on the modified Division of Microbiology and Infectious Diseases (DMID) criteria in [Appendix 5](#). Shift tables will be presented to show the number of subjects with a laboratory value with a grade of 0, 1, 2, 3 or 4 at baseline versus the value at each visit and the worst post-baseline value. Number and percentage of subjects with at least a 2 grade increase from baseline (based on DMID criteria) will be summarized by treatment arm. Percentages for each laboratory test will be based on the number of subjects with a baseline and post-baseline evaluation of the specific laboratory test. A listing

will be provided which gives all laboratory results for a given laboratory test for subjects who have at least a 2 grade increase from baseline.

The number and percentage (based on the number of subjects with a normal level at baseline) of subjects in each treatment group with an elevated transaminase level ($> 3 \times \text{ULN}$, $> 5 \times \text{ULN}$, and $>10 \times \text{ULN}$), an elevated bilirubin level ($>1.5 \times \text{ULN}$ and $>2 \times \text{ULN}$) will be presented by study visit. A table will list all subjects with any post-baseline ALT or AST $> 3x \text{ULN}$ or total bilirubin $>1.5 \times \text{ULN}$. The table will provide the AST, ALT, total bilirubin and alkaline phosphatase value for each subject at each time point laboratory values were entered. A listing of subjects who meet the laboratory criteria for Hy's law will also be provided. The laboratory criteria for Hy's law is defined as 1) ALT or AST $> 3 \times \text{ULN}$, ALP $\leq 2.0 \times \text{ULN}$, and total bilirubin $> 1.5 \times \text{ULN}$ and 2) ALT or AST $> 3 \times \text{ULN}$, ALP $\leq 2.0 \times \text{ULN}$, and total bilirubin $> 2 \times \text{ULN}$.

Detailed subject listings of all laboratory data (local and central laboratory data) collected during the study will be provided, including calculated creatinine clearance (using the Cockcroft-Gault equation). Laboratory values outside normal limits will be identified in the subject data listings with flags for low (L) and high (H) as will laboratory values that meet the clinically notable thresholds (CN).

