- ^b Day 1 is the first day of test article administration. Subsequent study days are consecutive calendar days.
- ^c A Day 10 visit should be conducted for subjects with treatment extending beyond 9 days, unless this visit coincides with the EOT visit.
- ^d To be conducted on the calendar day of, or within 2 days following the last dose of test article. Should also be conducted for any subject who withdraws prematurely or terminates participation in the study before completion.
- ^e To be conducted 7 to 14 days after the subject's last day of study therapy.
- ^f To be conducted 30 to 37 days after the first dose of test article. The Final Follow-up assessment may be conducted via telephone contact or by another interactive technology for subjects who were considered to be Clinical Successes and had no AEs or clinically significant laboratory or ECG abnormalities noted at or after the PTE visit. Otherwise, the visit must be conducted in person.
- ^g Written and signed ICF must be obtained before any assessment is performed.
- ^h Treatments that have been administered within the 7 days prior to the date of signing the ICF or during the Screening phase will be recorded in the eCRF. All medications and significant non-drug therapies (including physical therapy and blood transfusions) administered after the first dose of test article must be recorded in the eCRF.
- ⁱ Semi-quantitative description of infection features. Must be assessed within 48 to 72 hours after the first dose.
- ^j Measurement of the subject's lesion by ruler length × width. The Screening measurement must be collected within 4 hours prior to randomization. A lesion measurement must be completed within 48 to 72 hours after the first dose.
- ^k Diagnosis of the type of ABSSI (wound infection, cellulitis/erysipelas or major abscess) and anatomical location. A digital photograph of the infection site will be taken at Screening only.
- ^l A full physical examination will be completed at Screening; thereafter only changes from Screening measurements should be recorded as AEs in the eCRFs.

- ^m Blood pressure and pulse rate should be measured within 30 min before, and approximately (\pm 15 minutes) 1 hour after and 3 hours after the completion of the first dose on Day 1.

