Omadacycline is very active *in vitro* against most Gram-positive pathogens. It also exhibits activity against atypical pathogens (eg, *Legionella* spp.), and some anaerobic and Gram-negative pathogens. The drug is active against strains expressing both mechanisms of tetracycline resistance as well as strains that are resistant to currently available antibiotics, including methicillin, vancomycin, erythromycin, and ciprofloxacin.²

Omadacycline has been developed for both iv and po administration and to date over 700 subjects have received one or both formulations in clinical studies. Across the completed Phase 1 studies, more than 500 subjects were exposed to omadacycline.

Single iv doses up to 600 mg and single po doses up to 600 mg have been investigated. Multiple iv doses of 100 mg once daily and 200 mg once daily for up to 14 and 7 consecutive days, respectively, have been investigated. Multiple po doses of 200 mg once daily and 300 mg once daily for up to 10 consecutive days have also been investigated. In a Phase 2 study, 219 subjects

with complicated skin and skin structure infections (cSSSI) were treated with omadacycline (n = 111) or linezolid (n = 108); treatment was initiated with iv administration, with switch to po therapy at the discretion of the investigator. In this study the total duration of study treatment was a mean of 10 and maximum of 20 days. In a sponsor terminated Phase 3 study of similar design, 140 subjects with cSSSI were treated with omadacycline (n = 68) or linezolid (n = 72) for a mean of 10 and maximum of 20 days for omadacycline and 22 days for linezolid.

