In the sponsor-terminated Phase 3 cSSSI study, 140 subjects were treated prior to the sponsor's decision to discontinue the study (due to changing regulations regarding the endpoints). The overall incidence of reported AEs in this study was comparable between the 2 treatment groups. The most commonly reported AEs (greater than or equal to 10% frequency in either treatment group) were nausea (27% omadacycline, 26% linezolid), headache (24% omadacycline, 7% linezolid), vomiting (9% omadacycline, 15% linezolid), diarrhea (4% omadacycline, 18% linezolid), and dizziness (10% omadacycline, 8% linezolid). Creatine phosphokinase (CK) elevation was reported in 9% of omadacycline treated subjects compared to 3% for linezolid. Alanine Aminotransferase increases were reported as AEs in 1 omadacycline subject (2%)

compared to 4 linezolid treated subjects (6%). Rash was reported by 1 omadacycline subject (2%) and 6 linezolid subjects (8%). Serious adverse events (SAEs) were experienced by 3 omadacycline subjects (small bowel obstruction, large left pleural effusion, and worsening depression) and 1 linezolid subject (worsening right hand cellulitis).

In a completed Phase 3 study comparing omadacycline and linezolid for the treatment of adults with ABSSSI (PTK0796-ABSI-1108), subjects started therapy with omadacycline 100 mg iv every 12 hours (q12h) for 2 doses then 100 mg iv every 24 hours (q24h), or linezolid 600 mg iv q12h. Subjects could be switched to oral therapy (omadacycline 300 mg q24h or linezolid 600 mg q12h) after a minimum of 3 days of iv therapy; the total treatment duration was 7-14 days. Study results showed that omadacycline was non-inferior to linezolid. In the modified intent-to-treat population (mITT, total N=627) for omadacycline versus linezolid, respectively, clinical success based on a reduction of lesion size at 48-72 hours after the first dose was 84.8% versus 85.5% (95% confidence interval [CI]: -6.3, 4.9); clinical success based on investigator's assessment of clinical response at 7-14 days after the last dose was 86.1% versus 83.6% (CI: -3.2, 8.2). Omadacycline was well tolerated: treatment-emergent adverse events (TEAEs) were reported in 48.3% versus 45.7%; serious TEAEs in 3.4% versus 2.5% and discontinuation due to TEAE in 1.9% versus 2.2% of omadacycline and linezolid treated subjects, respectively.

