16.1.2 Laboratory Evaluations

Blood samples for hematology, serum chemistry and coagulation (prothrombin time only) should be drawn at the Screening, Day 3, Day 7, Day 10, EOT, and PTE visits (see [Section 8](#)). At Screening only, 1 sample will be analyzed at a local laboratory for confirmation of eligibility criteria and a second sample shipped to the Central Laboratory for analysis. All other visits should have samples shipped to the Central Laboratory for analysis.

The Central Laboratory will be used for safety analysis of all specimens collected. Details on the collection tubes and containers, shipment of samples and reporting of results by the Central Laboratory are provided to investigators in the Central Laboratory manual.

Because subject enrollment will not permit using Central Laboratory results to assess a subject's meeting inclusion/exclusion criteria, it is expected that local laboratory testing will be used in circumstances where this testing is needed to assess a subject's WBC count or differential, serum transaminase or bilirubin levels, serum creatinine or pregnancy testing (for women only).

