16.1.2.2 Clinical Chemistry

The analytes indicated in Table 4 below will be measured at the Central Laboratory.

Table 4. Clinical Chemistry Panel

Blood glucose	ALT	LDH
Urea	AST	CK
Creatinine	AP	(CK isoenzyme testing as required)
Sodium	Total bilirubin	Calcium
Potassium	Total protein	Phosphate
Chloride	Magnesium	Cholesterol
Bicarbonate	Albumin	Uric Acid
		GGT
		Amylase
		Lipase

ALT = Alanine aminotransferase; AP = Alkaline phosphatase; AST = Aspartate aminotransferase;
 CK = creatine phosphokinase; GGT = gamma-glutamyl transpeptidase; LDH = Lactate dehydrogenase.

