Appendix 4 Directionality of Worst Laboratory Parameters

Laboratory Test	Parameter	Worst Value
Hematology	Hematocrit	Lowest value
	Hemoglobin	Lowest value
	Red blood cell count	Lowest value
	Mean cell hemoglobin	Lowest value
	Mean cell hemoglobin concentration	Lowest value
	Mean cell volume	Lowest value
	White blood cell count	Lowest value
	Platelets	Lowest value
	Neutrophils	Lowest value
	Lymphocytes	Lowest value
	Monocytes	Lowest value
	Eosinophils	Highest value
	Basophils	Lowest value
	Chemistry	Albumin
Alkaline phosphatase		Highest value
Alanine aminotransferase ALT/SGPT)		Highest value
Amylase		Highest value
Aspartate aminotransferase (AST/SGOT)		Highest value
Urea		Highest value
Bicarbonate		Lowest value
Calcium		Both highest value and lowest value
Cholesterol		Highest value
Chloride		Both highest value and lowest value
Creatinine		Highest value
Creatine kinase (CK)		Highest value
Gamma-glutamyl transpeptidase (GGT)		Highest value
Blood glucose		Both highest value and lowest value
Lactate dehydrogenase (LDH)		Highest value
Lipase		Highest value
Magnesium		Both highest value and lowest value
Phosphate		Both highest value and lowest value
Potassium		Both highest value and lowest value
Sodium		Both highest value and lowest value
Total bilirubin		Highest value
Total protein		Lowest value
Uric acid		Highest value
Coagulation	International normalized ratio (INR)	Highest value

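### SAP Appendix 5, the only source of clinically notable laboratory criteria, has no creatine kinase (CK) row, so the plan gives no by-arm, threshold-based CK incidence that does not depend on investigator judgement

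*SAP*

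**What the plan says.** **Background.** In the account of the sponsor-terminated Phase 3 cSSSI study, Protocol 9.1 reports: "Creatine phosphokinase (CK) elevation was reported in 9% of omadacycline treated subjects compared to 3% for linezolid". The same section gives the arm sizes as 68 omadacycline and 72 linezolid.

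**Collection.** CK is in the central chemistry panel (Protocol 16.1.2.2, Table 4), with isoenzyme testing as required. Under Protocol 16.1.2, chemistry samples "should be drawn at the Screening, Day 3, Day 7, Day 10, EOT, and PTE visits". Day 10 is conditional. A footnote to the Protocol section 8 flowchart reads "A Day 10 visit should be conducted for subjects with treatment extending beyond 9 days", unless that visit coincides with EOT. A subject therefore has up to six scheduled CK values.

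**Criteria.** Protocol 22.7.4 plans a by-visit summary of clinically notable laboratory values and leaves the criteria to the SAP. SAP 11.4 responds: "Clinically notable laboratory values will be determined based on the modified Division of Microbiology and Infectious Diseases (DMID) criteria", pointing to Appendix 5. It builds four outputs on those criteria: grade shift tables, the number and percentage with a rise of 2 or more grades, a listing of those subjects, and a clinically notable flag.

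**Where CK appears in the SAP.** Table 9 lists it under other chemistry, and Appendix 4 takes its highest value as the worst. It is in no block of Appendix 5.

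**The concern.** An analyte with no grade row cannot enter any output built on grades. However high a subject's CK, the value has no grade, cannot shift grade, cannot rise by 2 grades and cannot be flagged as clinically notable.

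Other chemistry parameters are also ungraded. CK stands out because it is the only ungraded one for which the protocol itself reports a higher rate on omadacycline. This trial is about five times the size of the earlier study (704/140 = 5.0) and measures CK centrally and repeatedly under blinding. It could show whether the earlier difference recurs, but the plan prespecifies no laboratory count that would do so.

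What is at stake is the clarity of one safety summary. If CK thresholds are chosen after unblinding, the result can be challenged as post hoc, whether it reassures or not.

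**Working it through.** **1. The earlier figures as counts.** Inputs: 9% of 68 and 3% of 72 (Protocol 9.1).
- 6/68 = 8.8%, which rounds to 9%. 5/68 = 7.4% and 7/68 = 10.3% do not.
- 2/72 = 2.8%, which rounds to 3%. 1/72 = 1.4% and 3/72 = 4.2% do not.
- So the counts are 6 and 2. The difference is 8.82% − 2.78% = 6.0 percentage points.

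**2. How firm that difference is.** With 8 events among 140 subjects and 68 on omadacycline, the two-sided Fisher exact p sums the hypergeometric probabilities no larger than that of the observed split (6 on omadacycline):
- 6, 7 or 8 events on omadacycline: 0.0937 + 0.0234 + 0.0025
- 0 or 1 event on omadacycline: 0.0040 + 0.0336
- Total: p = 0.157

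The score 95% confidence interval for the difference runs from about −2 to +15.5 points. The data fit both no difference and a sizeable one.

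**3. Table 9 against Appendix 5.** SAP Table 9 has 24 chemistry parameters.

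| | Parameters | Number |
|---|---|---|
| Graded in Appendix 5 | Sodium, potassium, glucose, calcium, magnesium, phosphate, total bilirubin, urea, uric acid, creatinine, AST, ALT, GGT, alkaline phosphatase, amylase, lipase | 16 |
| Not graded | Bicarbonate, chloride, albumin, cholesterol, CK, CK isoenzyme, LDH, total protein | 8 |

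The Enzymes block has six intact rows: AST, ALT, GGT, alkaline phosphatase, amylase and lipase. Nothing suggests that a row was lost when the PDF was read.

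**4. Other thresholds in SAP 11.4.** The remaining numeric cut-offs are for transaminases (above 3, 5 and 10 × ULN), bilirubin (above 1.5 and 2 × ULN) and the Hy's law criteria, which add alkaline phosphatase. None covers CK. For comparison, ALT increases reported as adverse events in the same earlier study were less frequent on omadacycline (2% vs 6%). ALT nevertheless has both grades and ULN-multiple counts.

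**5. What the plan still produces for CK.**

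| Output | By arm? | Fixed laboratory threshold? | Independent of investigator judgement? |
|---|---|---|---|
| Descriptive statistics: value, change, worst value (SAP 11.4) | Yes | No | Yes |
| High flag in subject listings (SAP 11.4) | Not tabulated | Yes, normal range | Yes |
| Adverse event tables by preferred term (SAP 11.1) | Yes | No | No (Protocol 21.2.4) |
| Grade shifts, 2-grade rise, clinically notable flag | CK absent | – | – |

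No row has a yes in all three columns for CK.

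**The case against.** **The earlier data are weak.** The protocol gives the CK figures within an adverse event summary and calls overall incidence comparable between arms. Protocol 9.1 also reports no pattern of adverse laboratory changes in the Phase 2 study (111 vs 108 subjects), and its summary of the completed Phase 3 ABSSSI study does not mention CK. A reader might infer that CK elevation is an established omadacycline signal. The documents do not support that: 6/68 vs 2/72 gives p = 0.16, and neither document names CK as an event of special interest. This part of the objection stands in full.

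**CK is not left unanalysed.** A reader might infer that the plan reports CK only through means and ranges. That is wrong. CK elevations reported as adverse events are counted by arm, by preferred term, severity and relationship. Those tables may be the like-for-like comparison with the earlier 9% vs 3%. The worst-value summary includes the median and maximum, so extreme values would be visible. What the objection does not meet is step 5. Protocol 21.2.4 limits adverse event recording of laboratory abnormalities to those judged clinically significant, outside the expected range and not part of another diagnosis.

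**Projecting the old rates.** With 352 per arm, 352 × 6/68 is about 31 and 352 × 2/72 is about 10. It is tempting to set these against an absence of graded CK events. The comparison fails because it puts adverse event rates beside laboratory grades. If those rates recurred as adverse events, the preferred-term tables would show them. The earlier study also started treatment intravenously, whereas this one is oral only.

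**CK was not singled out.** Seven other chemistry parameters are ungraded, and Protocol 22.7.4 does not require a criterion for every analyte. This stands, and it makes the point an improvement rather than the correction of a contradiction.

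**Conclusion.** The point holds as a gap in a safety summary. CK has no row in the only table that defines clinically notable laboratory values, so it cannot enter the shift tables, the 2-grade rise table and listing, or the clinically notable flag. The remaining outputs give no by-arm CK incidence that is both threshold-based and independent of investigator judgement.

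The size is modest. One analyte is affected, measured at up to six scheduled visits, and no efficacy or decision-bearing analysis changes. The case for acting is that the protocol reports a 6-point imbalance too imprecise to interpret, while this larger trial collects the data that could clarify it. No figure for the eventual CK incidence can be given, because the documents contain no CK cut-offs and the earlier rates come from adverse event reporting. The conclusion assumes that Appendix 5 is complete as shown.

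**What to change.** Before unblinding, do one of the following:

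- Add a CK row to the Enzymes block of SAP Appendix 5 in multiples of ULN. The AST/ALT bands already there (below 1.25, 1.25 to 2.5, above 2.5 to 5, above 5 to 10, above 10 × ULN) would serve as an example. The documents give no CK cut-offs, so the sponsor should choose and confirm the bands. CK then enters all four grade-based outputs.
- Or add by-arm CK counts at prespecified multiples of ULN to SAP 11.4, as is done for transaminases.

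Either way, these are reporting bands only and carry no treatment rule. Timing allows it: Protocol 22 and 25.3 require the SAP to be final before database lock, and the sponsor has already adapted Appendix 5 by adding Grade 0 and closing numeric gaps in the enzyme bands.

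The cost is one table row or sentence, a few more output lines, and some non-specific flagged values. In a randomised, double-blind comparison those are expected equally in both arms.
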